Participants will be randomized to a MedDiet program or the currently offered American College of Obstetricians and Gynecologists (ACOG)-based dietary counseling program at Myers Park and North Park OBGYN Clinic(s) in Charlotte, North Carolina.

Duration of Study and Participating Site

This will be a multi-center study including Myers Park OB/GYN Clinic and North Park OB/GYN Clinic which are academic obstetrical practices providing prenatal care to a socially vulnerable and highly racial/ethnic diverse population. All new scheduled prenatal visits will be screened in Epic for eligibility by our research team.

We anticipate full completion of the study by July 2025.

Study population (Table 1)

Inclusion Criteria	Exclusion Criteria

• Viable singleton pregnancy in the first trimester (6 0/7- 16 6/7 weeks); includes twins reduced to singleton spontaneously or vanishing twin syndrome• BMI $\geq 25.0 \text{ kg/m}^2$; calculated by dividing maternal weight in kilograms by height in meters squared using a calibrated scale and standard metric measure (BMI calculator available at www.cdc.gov)• Confirmed intrauterine pregnancy by ultrasound exam (6-16 weeks)• Age 18 years or older• Primary language of English or Spanish	
• BMI $< 25.0 \text{ kg/m}^2$• Known pre-pregnancy diabetes• Hemoglobin glycosylated (A1C) $> 5.7\%$ at first prenatal visit• Pre-pregnancy hypertensive disease• Non-viable pregnancy• Known allergies to an essential component(s) of MedDiet• Inability to read or write in primary language• Mental incapacity to make medical decisions• Food insecurity

Sample Size

Since this is a pilot study, we aim to enroll 60 participants with 30 per study arm. Based on the patient population at Myers Park, we anticipate the following racial/ethnic breakdown of subjects.

Table 2 Anticipated Enrollment (all subjects will be female)

Race	Non-Hispanic	Hispanic	Total
Asian	1	0	1
Black or African American	15	0	15
White	6	36	42
More than One Race	2	0	2
Total	24	36	60

Methods and Intervention

- Fig 1 and Table 3 provide a detailed view of the study activities.
- With the purpose of overcoming language barriers, the dietary program was developed in English and Spanish. Multiple aids were created including practical educational tools, recipes, shopping list, and meal portion guidance to improve engagement and enhance sustainability.

Randomization and Study Groups:

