- Following informed consent and eligibility confirmation, subjects will be randomized in blocks of 4 using a single sequence computer-generated random number⁴⁰ to balance for baseline BMI category (overweight or obese Random allocation number assigned to MedDiet program (intervention group) or ACOG-based nutritional counseling (control group) will be in a sealed opaque envelope.
 - Subjects allocated to the ACOG-based Dietary Program (Control Group) will receive:
 - Following ACOG recommendation, routine counseling on healthy eating will be provided. This will include advice on the consumption of grains, fruits, vegetables, protein, and dairy foods recommended during pregnancy ([Nutrition During Pregnancy | ACOG](#))⁴¹ (www.myplate.gov). (Appendix A-F (English)/Appendix G-L (Spanish))
 - Diet adherence will be assessed using a Routine Diet Adherence Questionnaire (Appendix M (English)/Appendix N (Spanish)).
 - Six traditional healthy meals will be shipped by ModifyHealth LLC directly to the participant's home every 3 weeks between enrollment and until the subject is approximately 38 weeks pregnant.
 - Participants will receive canola oil and a healthy snack during their enrollment visit and during their routine 26-30 week prenatal visit
 - Subjects allocated to the MedDiet Program (Intervention Group) group will receive:
 - Counseling based on the principles of the traditional MedDiet²⁷ with a focus on a general change in diet instead of micronutrients or macronutrients. (Appendix O-P;SS-UU (English)/Appendix Q-R; VV-XX (Spanish))
 - Diet adherence will be assessed using a modified version of the validated MedDiet Adherence Questionnaire.³⁹ (Appendix S (English)/Appendix T (Spanish))
 - Six traditional MedDiet meals will be shipped by ModifyHealth LLC directly to the participant's home every 3 weeks between enrollment and until the subject is approximately 38 weeks pregnant.
 - Participants will receive olive oil and nuts during their enrollment visit and during their routine 26-30 week prenatal visit.

Baseline Visit:

- All subjects will participate in a 30-minute baseline Nutritional Assessment and Diet Counseling Session regardless of the arm they are randomized to. This will occur during their initial prenatal visit at 6-16 weeks of pregnancy. The following items will be covered in this visit:

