Approximately 30 new prenatal visits are scheduled in our clinic weekly and we anticipate 10 of those patients will be eligible. All pregnancy confirmation visits will be screened by a research member (PI, Co-PI, study coordinator) in Epic to establish eligibility. The following PHI will be collected for screening purposes:

- Name
- MRN
- Age
- BMI
- Diagnosis of pre-pregnancy diabetes
- Hemoglobin glycosylated (A1C) value at pregnancy confirmation visit
- Diagnosis of pre-pregnancy hypertensive disease
- Confirmation of viable singleton pregnancy
- Gestational age of pregnancy
- Primary language of English or Spanish
- Food allergies

Screening data will be entered into an Excel spreadsheet stored on a secure drive which only the research team will have access to.

At the first prenatal visit, women who meet inclusion/exclusion criteria will be presented a flyer (Appendix NN (English)/ Appendix OO (Spanish)) and invited to participate in the study. Eligibility will be confirmed following informed consent and the Eligibility Form will be completed (Appendix PP).

Informed Consent

At the first prenatal visit, women who meet inclusion/exclusion criteria will be invited to participate in the study. Signed informed consent (Appendix QQ (English)/Appendix RR (Spanish))) will be obtained from each subject by a member of the research team. If the

research member obtaining consent is not fluent in Spanish, an interpreter will be used. Consent will be obtained in a private room with a closed door in the clinic during the subject's initial prenatal visit. Participants will be fully informed about the nature of the study and the potential risks of the dietary intervention, anticipated to be minimal as this is a behavioral intervention.

Spanish Speaking Subjects

All study related materials will be available in both English and Spanish. Qualified and trained Spanish language medical interpreters will be used to communicate with Spanish language participants if the investigators are not proficient in speaking Spanish.

Confidentiality and Privacy

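### A fixed, disclosed block size of 4 leaves allocation concealment incomplete: up to about a third of allocations can be known in advance

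*Combined protocol and SAP*

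**What the plan says.** Randomization and Study Groups describes the method: "subjects will be randomized in blocks of 4 using a single sequence computer-generated random number", the aim being "to balance for baseline BMI category (overweight or obese". The allocation "will be in a sealed opaque envelope". Randomization comes "Following informed consent and eligibility confirmation". Sample Size gives the total: "we aim to enroll 60 participants with 30 per study arm".

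The same section lists what each arm receives. The counselling differs, and at the enrollment visit one arm is given olive oil and nuts while the other is given canola oil and a snack. No blinding is described.

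On recruitment, Screening and Recruitment says: "All pregnancy confirmation visits will be screened by a research member (PI, Co-PI, study coordinator) in Epic to establish eligibility". Informed Consent assigns consent to a member of the research team. Both sections say that women who meet the criteria will be invited.

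On sites, Duration of Study and Participating Site says: "This will be a multi-center study including Myers Park OB/GYN Clinic and North Park OB/GYN Clinic".

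The protocol does not say:
- who prepares, holds or opens the envelopes, or whether they are numbered;
- whether the two clinics share a list;
- how one sequence is meant to balance BMI category;
- whether the block size is kept from recruiting staff.

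**The concern.** A sealed envelope hides the card, but not what can be deduced from the cards already opened. In a 1:1 block of 4 each arm has two places. Once one arm has used both, the rest of the block is fixed. Here the arm is visible at the enrollment visit and the block size is in the protocol that study staff hold, so a recruiter who keeps a tally can know the next assignment before approaching the next woman.

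What is at stake is selection bias. A woman who seems motivated could be approached sooner, or more warmly, when the next place is known to be MedDiet. Motivation plausibly affects adherence and gestational weight gain. It is not among the listed baseline items, so regression adjustment cannot be relied on to remove its effect. The comparisons most exposed are the secondary ones between arms: gestational weight gain, adverse pregnancy outcomes and biomarkers. MedDiet adherence, part of the primary objective, is exposed to a lesser extent, because steering could raise it within that arm.

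**Working it through.** The plan gives no figure for predictability, so there is none to reproduce.

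**Inputs from the protocol.** Block size 4, ratio 1:1, N = 60, hence 60/4 = 15 complete blocks on one list; two clinics; balance on BMI category.

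**Assumptions.** Unless stated otherwise, staff know the block size and every earlier allocation on the list. Splits between clinics and between BMI categories are not given, so a range is shown.

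**1. Certain allocations, full history known.** There are 6 equally likely blocks of 4.
- Places 1 and 2: never certain.
- Place 3: certain if the first two match, probability 2/6 = 1/3.
- Place 4: always certain.

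Expected share = (0 + 0 + 1/3 + 1)/4 = 33.3%, and 60 × 1/3 = 20. Each block has one or two certain places, so the possible range is 15 to 30; simulation puts about 95% of lists between 17 and 24.

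**2. Best guess, full history known.** Guessing the arm used less so far in the block is right with probability 1/2, 2/3, 2/3 and 1 at the four places. The sum is 2.833, and 2.833/4 = 70.8% (42.5 of 60), against 50% with no information.

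**3. Separate lists.** By simulation with 60 women, full history known and equal splits assumed:
- two BMI lists: 32.0% certain;
- BMI by clinic (four lists): 30.5% certain.

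The unclear list structure therefore matters little if the history is known.

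**4. One list shared by two clinics, each seeing only its own allocations.** Let s be one clinic's share of enrollment. The next place is certain only if both used places of the exhausted arm were filled at the clinic now recruiting, which multiplies the result in step 1 by q = s³ + (1 − s)³. Certain share = q/3.

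| Clinic split | q | Certain |
|---|---|---|
| 50/50 | 0.25 | 8.3% |
| 70/30 | 0.37 | 12.3% |
| 80/20 | 0.52 | 17.3% |
| 90/10 | 0.73 | 24.3% |

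**5. Effect of varied block sizes.** This assumes sizes drawn with equal probability and a guesser who knows the possible sizes and the full history. The certain share comes from simulated lists of 60. The hit rate is the expected number of correct guesses per block (1.5 for size 2, 2.833 for size 4, 4.1 for size 6) divided by places.

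| Design | Certain | Best guess right |
|---|---|---|
| Fixed 4 | 33.3% | 70.8% |
| 4 and 6 | about 6% (5.5%) | (2.833 + 4.1)/10 = 69.3% |
| 2, 4 and 6 | about 4% | (1.5 + 2.833 + 4.1)/12 = 70.3% |

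Varied sizes remove most of the certainty but little of the guessability. Guessing whichever arm is behind needs no knowledge of the sizes.

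**The case against.** The strongest reply has four parts.

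**A third is near a ceiling.** It requires staff to track every earlier allocation on the list, and the protocol does not show that they can or do. This stands: with a shared list and own-clinic knowledge only, the share is 8-24%.

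**The envelopes still work for most women.** A reader might infer that they conceal nothing. The documents do not support that. Even at the ceiling two thirds of allocations are not certain, and randomization follows consent and confirmed eligibility. That order does not answer the point entirely, since a deduction can be made before a woman is approached.

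**No discretion over invitation is written.** A reader might also infer that staff choose whom to invite, or that those who recruit also open the envelopes. The protocol says that women who meet the criteria will be invited, and it does not name who handles the envelopes. The estimate of about 10 eligible women a week is a volume figure, not evidence of selection. What remains is the possibility of influence through the timing or encouragement of an invitation.

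**It is a pilot, and fixed blocks give exactly 30/30 on one list.** The between-group results are described as preliminary, there is no sample-size calculation, and the size of any resulting bias cannot be estimated from the documents. This limits the severity. It does not remove the point, because the protocol intends the findings as the foundation for larger trials and the remedy is cheap.

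**Conclusion.** The concern holds as a weakness of degree: concealment is incomplete, not absent. With fixed blocks of 4, the certain share is one third in expectation (20 of 60) if all earlier allocations on a single list are known. It is 30-32% under separate BMI or BMI-by-clinic lists, and about 8-24% if two clinics share a list and see only their own allocations. Which applies cannot be settled from the protocol, because it does not state the list structure or who sees past allocations.

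The conclusion rests on the arms being recognisable once assigned, which follows from the different counselling and foods although the protocol does not call the trial open-label. It also rests on recruiting staff knowing the block size, which nothing in the protocol prevents. It does not show that selection will occur. The change is worth making before enrollment, or for the remaining enrollment.

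**What to change.** In Randomization and Study Groups, replace the fixed block size with permuted blocks of randomly varied size and do not state the sizes there. Sizes 4 and 6 would serve. Leave out 2, because the second place in such a block is always determined and the hit rate within it is 75%. Keep the sizes in a separate document, held by someone who neither screens nor consents.

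Release each allocation through REDCap, already used for the trial's data, only after consent and eligibility have been recorded there. State in the same section who holds the list, whether the clinics share it, and whether each BMI category has its own list.

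The change should be presented for what it does: certain allocations fall from up to a third to about 6%, while the best-guess rate stays near 69%.

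The cost is generating a new list and setting up the REDCap module. If enrollment stops mid-block, the arms can differ by up to 3 per list (half the largest block), against 2 with blocks of 4. On a single list closed at exactly 60 the difference must be even, so the worst split is 31/29.

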Pregnancy data collected*	X	X	X	X	X	X	X	X
Delivery data collected**								
Neonatal data collected**								

*Data will be collected through medical records

**Data will be collected at 6 weeks post-delivery through medical records.

Outcomes

- **Diet Adherence Assessment:** Adherence of both groups will be assessed with a questionnaire based on a validated diet adherence questionnaire³⁹ during counseling sessions as described above. Questionnaires will be scored with a “1” assigned to all responses corresponding to the recommended guidelines and a “0” assigned to all responses which do not correspond to the recommended guidelines. The level of adherence will be defined based on the scale score as: ≤4 low adherence, 5-11 moderate adherence, and ≥ 12 high adherence.
- **GWG:** Total GWG will be calculated by subtracting the participant’s weight (lbs.) at the initial prenatal visit from the weight (lbs.) at time of the delivery or at the last prenatal visit. GWG in the first trimester (6-13 weeks), second trimester (14-26 weeks), and third trimester (27-40 weeks) will also be calculated. Calibrated weight scales will be used at our clinic and at the hospital. Compliance rate of GWG based on IOM guidelines for overweight and obese women¹⁰ will be compared between the MedDiet and the control group.
- **Adverse Pregnancy Outcomes (APO):** We will examine the most common Adverse Pregnancy Outcomes (APO) associated with overweight and obesity (Table 3).^{2,4,5-7,45-51} Definition and management of all APO will follow the standardized guidelines at Myers Park OBGYN clinic.

Table 3 Adverse Pregnancy Outcomes (APO)

APO	Prevalence in Pregnant Women
HDP (preeclampsia, eclampsia, or gestational hypertension)	4-6% of overweight/obese women BMI ≥30 ⁴⁵ 12% in women with a BMI ≥40 ⁴⁶
GDM	6-14% in overweight/obese women ⁴⁷
PTB	10.2% in US in 2021 was 10.2% (www.cdc.gov); data suggest increased risk among overweight/obese women 48-50
Cesarean Delivery	29.9% in NC in 2020 (www.cdc.gov); There is a dose-response relationship between pre-pregnancy BMI and cesarean delivery rate. ^{4,7,51}
Large for Gestational Age (LGA) infant	Data suggestion relationship between LGA (birth weight >90th percentile) and overweight /obese women ^{7,51}

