- **Cardiovascular parameters:** MedDiet is associated with reduction of blood pressure (BP) in non-pregnant adult overweight or obese women.⁵² Physiological changes of blood pressure (BP) during pregnancy are characterized by reduction of BP in the second trimester with return to the pre-pregnancy level late in the third trimester and postpartum period.⁵³ Heart rate (HR) increases by 20% to 25% over baseline during gestation.⁵⁴ Maternal BP and HR will be obtained by a calibrated automated oscillometric device during prenatal visits from the first to the third trimesters following the standardized technique established in our clinic. Trends of BP and HR throughout gestation will be compared among women allocated in the intervention and the control groups.
- **Cardiometabolic biomarkers:** Consumption of MedDiet is associated with lower levels of total cholesterol,⁵³ reduces insulin resistance preventing type 2 diabetes^{30,31} and GDM,^{34,36} and reduces markers of subclinical inflammation such as C-reactive protein (CRP).⁵⁵ Pregnancy is characterized by increased levels of total cholesterol, low-density lipoprotein (LDL), high-density lipoprotein (HDL), and triglycerides, especially in the second and third trimester,⁵⁶ and pregnancy is a state of increased insulin resistance.⁵⁷ There is limited knowledge about the effect of MedDiet on cardiometabolic biomarkers during pregnancy. Maternal lipid profile, random glucose level, hemoglobin A1C, and CRP levels will be compared at baseline (6-16

weeks) and at 26-30 weeks of gestation among participants in the intervention and the control groups. The labs will be obtained at the same time of scheduled blood draws for routine prenatal labs.

Analytical Plan

This is prospective randomized pilot study of sixty participants who will be randomly allocated in the MedDiet group or in the control group. Because this is a pilot study, a sample size was not calculated. Results will be analyzed initially using descriptive statistics. Comparison between groups will be done using chi square tests for proportions, and t-tests or ANOVA procedures for continuous variables. Regression analysis will be performed to identify independent outcome predictors. Other inferential statistical analysis will be conducted as appropriate.

Human Subjects Protection

Screening and Recruitment

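### A single sequence in blocks of 4 fixes the arm totals but does not balance BMI category, and the between-arm comparisons are not adjusted for BMI category

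*Combined protocol and SAP*

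**What the plan says.** Under Randomization and Study Groups, the combined protocol and SAP states that women are "randomized in blocks of 4 using a single sequence computer-generated random number⁴⁰ to balance for baseline BMI category", with the two categories (overweight, obese) named in a bracket that is never closed. Allocations are placed in sealed opaque envelopes. The Sample Size section sets 60 participants, 30 per arm, and two clinics take part. Nowhere is a separate list or envelope set per BMI category described, nor minimization.

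The Analytical Plan begins with descriptive statistics and continues: "Comparison between groups will be done using chi square tests for proportions, and t-tests or ANOVA procedures for continuous variables". It adds that "Regression analysis will be performed to identify independent outcome predictors", without naming covariates, and leaves other inferential analysis to judgment. No adjustment or stratification by BMI category is stated.

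BMI category enters one outcome by definition. "Compliance rate of GWG based on IOM guidelines for overweight and obese women" is compared between arms, and the IOM ranges are 15-25 lb for overweight and 11-20 lb for obese women. For cesarean delivery, the Adverse Pregnancy Outcomes table says: "There is a dose-response relationship between pre-pregnancy BMI and cesarean delivery rate".

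**The concern.** The plan claims a property that the described method does not have. Permuted blocks equalize whatever is counted within the block. With one sequence, that is the number of women per arm and nothing else. To balance BMI category, the blocks must run separately within each category.

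A reader of the eventual report could therefore take BMI category as balanced by design when it was not. A visible imbalance would make the weight-gain and cesarean comparisons harder to interpret, and the plan has no prespecified adjustment to fall back on. The investigators chose BMI category as the factor to balance, so by their own reasoning it belongs in the analysis. If the lists are in fact stratified, the analysis still leaves the factor out, and the unadjusted t-test then overstates its standard error slightly.

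**Working it through.** **Inputs from the documents:** N = 60, 30 per arm, blocks of 4, two BMI categories, IOM ranges of 15-25 lb and 11-20 lb.

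**Assumptions (not in the documents):** obese share p from 0.3 to 0.7; within-category SD of weight gain 10 or 15 lb; a gap of 4.5 lb between categories. The gap is the difference of the range mid-points, (15+25)/2 − (11+20)/2 = 20 − 15.5. These are counseling targets, so the gap is only illustrative.

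**1. Arm totals.** 60/4 = 15 complete blocks with 2 women per arm in each, so 15 × 2 = 30 per arm. The planned 30/30 is reproduced.

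**2. BMI split under one sequence.** BMI category is unrelated to position in the list, so the obese counts in the two arms are independent Binomial(30, p). Their difference D has SD = √(60·p·(1−p)). Exact results:

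| Obese share | SD of D | Mean of absolute D | Differ by 4 or more | Differ by 6 or more |
|---|---|---|---|---|
| 30% or 70% | 3.55 | 2.82 | 32.3% | 12.0% |
| 40% or 60% | 3.79 | 3.01 | 35.6% | 14.7% |
| 50% | 3.87 | 3.08 | 36.6% | 15.5% |

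A difference of 6 is, for example, 18/30 against 12/30, or 20 percentage points. A simulation of 200,000 trials per setting agrees with the table.

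**3. BMI split under two lists.** Only the last, incomplete block of a list can be unequal, and a part-filled block of 4 is at most 2 apart. So D is at most 2 whatever the obese share.

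**4. Shift in weight gain caused by an imbalance.** Shift = gap × D/30. For D = 3 this is 4.5 × 3/30 = 0.45 lb; for D = 6 it is 4.5 × 6/30 = 0.9 lb. The standard error of the arm difference is about √(2·SD²/30): 2.6 lb at SD 10 and 3.9 lb at SD 15.

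**5. Gain from adjustment under one sequence.** The unadjusted variance is (SD² + gap²·p(1−p))/15. At p = 0.6 and SD 10 this is (100 + 20.25 × 0.24)/15 = 104.86/15, a standard error of 2.64 lb. Simulation gives 2.65 lb unadjusted and 2.62 lb adjusted. Over the settings with a 4.5 lb gap, adjustment lowers the SD of the estimate by 1.1-1.6% (SD 10) and 0-0.3% (SD 15). The unadjusted test rejects at 4.8-5.2% under the null, so its level is kept. The mean estimate is within 0.03 lb of zero.

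**6. Level of the unadjusted test under stratified lists.** The true variance is close to SD²/15, but the t-test still uses (SD² + gap²·p(1−p))/15. At p = 0.6 and SD 10 the standard error is too large by √1.0486 = 1.024. The effective critical value is 2.00 × 1.024 = 2.05 on 58 degrees of freedom, which gives a rejection rate of 4.5%. Simulation over the obese shares gives 4.4-4.6% at SD 10 and 4.7-4.8% at SD 15, against 4.9-5.2% with BMI category as a covariate.

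**The case against.** The strongest objection is that the sentence is broken exactly where the balancing factor is described. Balancing for BMI category is natural wording for stratified blocks, and words may have been lost. This stands in part: the imbalance figures apply only if one sequence is really used. It does not remove the point, because the text says a single sequence and no other section corrects it. Under the stratified reading the analysis still omits the stratifying factor.

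A second objection is that this is a pilot with no calculated sample size, a primary aim of feasibility and adherence, and room for further analyses as appropriate. This supports a low grade. But an open-ended allowance is not a prespecified adjustment, and neither is a regression aimed at finding predictors.

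Three stronger readings are tempting and are not supported:

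- *That the comparison is biased.* Randomization remains valid, and chance imbalance averages to zero.
- *That hypertensive disorders would be distorted by an overweight/obese imbalance.* The table gives 4-6% against a threshold of BMI 30 or more, and "12% in women with a BMI" of 40 or more. By its printed thresholds that contrast lies within the obese category and shows no difference between overweight and obese women. The cesarean statement is relevant, but gives no size.
- *That weight-gain compliance ignores BMI.* It is already judged against category-specific ranges, although that defines the outcome and does not adjust the comparison.

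**Conclusion.** The point holds as a minor one. As written, the method secures 30/30 totals and not BMI balance. At an assumed 30-70% obese, 32-37% of trials would differ by 4 or more obese women and 12-15.5% by 6 or more, where separate lists allow at most 2.

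The consequence is mainly for interpretation and credibility. For an assumed 4.5 lb gap, even a 6-woman imbalance moves the weight-gain difference by 0.9 lb, well inside one standard error. Adjustment gains about 0-1.6% in SD under one sequence. If the lists are stratified, the unadjusted test rejects at about 4.4-4.8% instead of 5%. The effect falls on the secondary comparisons, mainly weight gain and cesarean delivery, and not on the primary adherence aim. The sizes rest on the assumed obese share, gap and SDs; that one sequence cannot balance BMI category does not depend on them.

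**What to change.** 1. **Randomization and Study Groups.** Replace the reference to a single sequence with: *two separate computer-generated permuted-block sequences (blocks of 4), one for overweight and one for obese women, each with its own sequentially numbered sealed opaque envelopes*. If each clinic holds its own envelopes, say that the lists are by clinic and BMI category. If a single sequence has already been used, delete the statement that it balances BMI category and report how the list was built.
2. **Analytical Plan.** Add: *Between-arm comparisons of continuous outcomes are adjusted for BMI category and, where one is measured, for the baseline value of the outcome.*

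The cost is a short edit in each section. BMI and the baseline laboratory values are already collected ("Maternal lipid profile, random glucose level, hemoglobin A1C, and CRP levels will be compared at baseline" and again at 26-30 weeks).

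The downside of separate lists is that exact 30/30 is no longer guaranteed. With two central lists the worst case is 32/28. Both lists must stop halfway through a block, which happens about 1 time in 4, with both half-blocks leaning the same way: 2 × (1/6)² × 1/4 = 1.4%, against 1.2-1.4% in simulation. If the lists are also split by clinic, the totals can be somewhat further apart: 4 or more in 8-9% of simulated trials.
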